1.0 OBJECTIVES AND ENDPOINTS

Objectives	Endpoints/ Measurements
Primary Objective	

 To observe the effect of the Sip2Sleep® product on sleep quality for participants with self-reported sleep disturbance 	
 Change in average sleep quality score by 1 point as measured by daily 10-point visual analogue rating scale (VAS) from baseline and 1 week of no product use
Secondary Objectives	

 To assess the effect of Sip2Sleep® product on symptoms of sleep disturbance To assess the effect of Sip2Sleep® product on anxiety To assess the effect of Sip2Sleep® product on the level of alertness during the daytime 	
 Change in Insomnia Sleep Index (ISI) by 4.5 points from baseline and 1 week of no product use Change in Generalized Anxiety Disorder-7 (GAD-7) by 4.5 points from baseline and 1 week of no product use Change in average level of alertness during the daytime score by 1 point as measured by daily 10-point visual analogue rating scale (VAS) from baseline and 1 week of no product use
Exploratory Objectives	

 To observe the change in sleep duration via personal health tracking wearable device To observe the change in sleep latency via personal health 	
 Change in average nightly sleep duration as measured via personal health tracking wearable device from baseline and 1 week of no product use Change in average nightly sleep

tracking wearable device
 
3. To identify improvements for future participant-centered study designs using feedback
	
latency as measured via personal health tracking wearable device from baseline and 1 week of no product use
 
3. Assessment of patient satisfaction survey of study experience including design and use of app-based data collection tools

---	--

2.0 INTRODUCTION: BACKGROUND INFORMATION & SCIENTIFIC RATIONALE

2.1 Introduction/Rationale for Development

Insomnia occurs in up to 50% of adults in the U.S., while chronic insomnia disorder is estimated to impair 10-15%.¹ Lack of quality and quantity of sleep negatively affects every part of an individual's life, both personally and professionally. Poor sleep is associated with various comorbidities including depression, stroke, cardiovascular disease, obesity, dementia and Alzheimer's disease, and increased risk of developing type 2 diabetes.^{2,3,4,5} Furthermore, there has been an increase in evidence of the long-term harm (i.e., increased risk of cognitive dysfunction and impairment such as Alzheimer's disease) of taking prescription sleep aids such as Ambien, Lunesta, benzodiazepines, and OTC sleep aids like Benadryl.⁶

Sip2Sleep[®] was developed in conjunction with a leading sleep physician who has focused efforts in assisting patients improve sleep problems and insomnia by identifying the root cause(s) of the issues. Sip2Sleep[®] uses a proprietary formula of Montmorency tart cherry extract and Venetron[®].

Montmorency tart cherry is a special kind of cherry that is known to provide a natural source of melatonin. The ruby red pigments in this specific cherry are proanthocyanidins, natural compounds that help increase the brain availability of tryptophan—an essential amino acid and precursor to the natural sleep aid serotonin. Proanthocyanidins inhibit an enzyme (indoleamine 2,3 dioxygenase) that degrades tryptophan, a known predictor of insomnia. The minimization of tryptophan degradation may allow tryptophan to work more effectively in the body while increasing bioavailability for serotonin synthesis, leading to a positive effect on sleep while improving mood and decreasing inflammation.^{7,8}

Researchers at Louisiana State University presented data in 2018 showing that drinking Montmorency tart cherry juice just twice a day for two weeks helped increase total sleep time by nearly 90 minutes among older adults with insomnia. Greater than 75% of participants reported a positive response to the cherry juice with a significantly reduced amount of time to initiate sleep and improved ability to maintain sleep.⁷

Venetron[®] is a patented, purified, powdered extract derived from the Rafuma leaf, *Apocynum venetum*, which is a safe botanical alternative to St. John's Wort. It helps insomnia by:^{9,10,11}

- Not affecting the CYP3A pathway in the liver that many OTC natural substances (St. John's Wort) and medications can impact. This means it does not increase the risk of side effects and other drug interaction
- Containing bioactive flavonoids
- Supporting serotonin concentrations in clinical trials by reducing the degradation of serotonin in the blood and brain, thus helping sleep and improving mood
- Producing a calming effect by acting on the GABA-ergic system

Together, Montmorency tart cherry extract and Venetron® are a powerful, natural solution to insomnia. They work synergistically to increase the presence of serotonin in the brain to improve sleep. Additionally, together they improve mood because Venetron® exerts a calming effect on the mind and helps the overactive mind relax for quicker, longer-lasting sleep.

2.2 Overview of and Rationale for the Study Design

The rationale for this study is to determine the effect of a consumer-grade, unique formula called Sip2Sleep®, which is a combination of Montmorency tart cherry extract and Venetron®, a patented, purified, powdered extract derived from the Rafuma leaf, *Apocynum venetum*, on sleep disturbance in adults. Because this product is currently available in the OTC market across the United States, a consumer-driven, decentralized observational clinical research study is well-suited for examining the effect of this formulation on sleep.

Sleep disturbance is highly prevalent and impacted by many interdependent variables. We will examine self-reported sleep disturbance in a broad age-range of adults who have chosen to use this product. The study will incorporate participant reported outcome questionnaires, daily surveys, and the participants' personal health tracking wearable device (e.g. Apple Watch, Fitbit, Smartwatch, etc.) to engage the participant in their sleep health and explore objective digital outcome measures of sleep. An important feature of this consumer-driven study design is to help individual consumers observe the effects of this product on their own sleep patterns during the study itself. There is no "doctor-patient" relationship as part of this research since the participant as a consumer is making the informed choice to take the product and take part in the observational process with self-reported measures. Findings from this study will contribute knowledge toward the design of future sleep research studies, the improvement of the Sip2Sleep® product formulation, and may help inform clinical recommendations for adults interested in using alternative products for sleep.

The following self-reporting measures are used in order to evaluate the effect of Sip2Sleep® in adults with self-reported sleep disturbance:

Surveys to reflect sleep quality, sleep latency, total sleep duration and level of alertness during the day to be distributed daily. Sleep quality and level of alertness during the day will be evaluated with a single 10-point visual analogue scale (VAS) and objective sleep data reflecting sleep latency and total sleep duration will be collected from personal wearable devices.

Insomnia Sleep Index (ISI) is a brief self-report instrument measuring the patient's perception of both nocturnal and diurnal symptoms of insomnia during the past two weeks. The ISI comprises seven items assessing the perceived severity of difficulties initiating sleep, staying asleep, and early morning awakenings, satisfaction with current sleep pattern, interference with daily functioning, noticeability of impairment attributed to the sleep problem, and degree of distress or concern caused by the sleep problem. Each item is rated on a five-point scale and the total score indicates the severity of insomnia, with a range of possible scores from 0-28. A score higher than 14 has been indicated to be the optimal cut-off for insomnia as a disorder. The ISI has been widely used in clinical and research settings as it is brief and easy to administer, and can provide valuable information for diagnosis and treatment planning. Research has found that the ISI is sensitive in detecting changes in the patient's perception of treatment outcome, and a good degree of convergence exists between the patient and the clinician's evaluation of insomnia severity.^{13,14}

Generalized Anxiety Disorder-7 (GAD-7) is a self-reported anxiety survey utilized in primary care consisting of a 7-item anxiety scale. The instrument is well supported to use in a general population and normative data can be used to compare a subject's GAD-7 score with those determined from a general population reference group, with evidence of significant reliability and validity with congruent agreement in self-reported and interviewer-administered versions of the

scale. GAD and Depression symptoms frequently occur together, but previous studies have supported via factor analysis that this measure can detect GAD and depression as distinct dimensions.¹⁵ This measure will be used in combination with other scales to observe self-reported effects on sleep disturbances and insomnia, such as anxiety or other psychiatric disorders.

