3.2 Eligibility

Participants must meet all the following criteria on screening examination to be eligible to participate in the study:

Inclusion

1. Age \geq 18 years old
2. Has self-reported sleep disturbance
3. Insomnia Severity Index (ISI) score of \geq 15 at screening
4. Interested in understanding more about the quality of their sleep and chose to use the Sip2Sleep product for sleep
5. Willingness to do a minimum of 1 week wash out of current OTC or other products for sleep (e.g. melatonin, anticholinergics)
6. Willingness to do a minimum of 1 week wash out of any cannabis products
7. Able to receive shipment of the product at an address within the United States
8. If taking prescription hypnotics (e.g. zolpidem, zaleplon, benzodiazepines) or other class of medication for sleep, must be on a stable dose for at least 4 weeks.
9. Able to read and understand English
10. Able to use a personal smartphone
11. Has and is able to use a personal health tracking wearable device (e.g., Apple Watch, Fitbit Smartwatch, Oura Ring, etc.)
12. Able to understand and provide informed consent
13. Able to complete study assessments over 5 weeks

Exclusion

1. Research participants who have no computer, smartphone, and internet access and/or do not use a computer or smartphone
2. Concomitant Therapies:
 - a. Participants taking daily prescription medication for sleep (for example, prescription hypnotics like zolpidem, zaleplon, benzodiazepines) not on a stable dose for at least 4 weeks
 - b. Participants receiving Cognitive Behavioral Therapy for Insomnia (CBTi)

- c. Participants receiving any investigational therapies or treatments
3. Other Illnesses or Conditions: Participants who have the following co-morbidities are excluded:
- a. Confirmed diagnoses of the following sleep disorders: Narcolepsy, Restless Leg Syndrome, Circadian Rhythm Disorders
 - b. Confirmed diagnosis of Sleep Apnea that is untreated or not well controlled
 - c. Current or prior psychotic disorder
 - d. Current or prior Substance Abuse Disorder
 - e. Current or prior cardiac dysrhythmias (for example, atrial fibrillation, supraventricular tachycardia)
 - f. Currently pregnant, planning to become pregnant in the next 1 month, or breastfeeding
 - g. Allergies or adverse reactions (for example, anxiety) to Montmorency tart cherry extract and/or Venetron®

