3.3 Duration of Participation and Overview of What is Expected from Participants

Participants will complete a 5-week study consisting of screening assessments, baseline scales and surveys, objective digital measure, 2 weeks of product use (1 week on - 1 week off - 1 week on), scales and surveys, and end of study assessments and surveys. This is a remote observational study that will use the People Science app-based data collection platform Consumer Health Learning and Organizing Ecosystem (CHLOE) for study participants to report their assessments and collect objective sleep data from personal wearable devices. Participants will receive the study product during the baseline period. Demographic and medical history data will be collected for the study.

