6.0 STUDY PROCEDURES

6.1 Study Overview

[figure not shown]

Figure 1. Study Design

Upon enrollment, the study assessments can be accessed via CHLOE mobile app available on Apple iOS and Android devices as well as any web browser. The participant's activities are as follows:

Screening (Day -7 to Day -1):

- Informed Consent
- Complete demographic and medical history data intake.
- Screening Insomnia Severity Index (ISI) assessment.
- Provide preferred shipment address for product shipment during Baseline.

Baseline Period (Day 1 to Day 7):

- Complete Insomnia Severity Index and Generalized Anxiety Disorder-7 (Day 1 only).
- Begin discontinuation of non-prescription products used for sleep.
- Begin nightly use of personal health tracking wearable device through Day 28.
- Complete daily survey to review objective data (sleep duration and sleep latency) from wearable device collection and answer questions about their prior night's sleep quality and level of alertness since waking.
- Receive shipment of study product and instructions for use.

Product Use Period (Day 8 to Day 14):

- Complete Insomnia Severity Index and Generalized Anxiety Disorder-7 (Day 8 only).
- Continue nightly use of personal health tracking wearable device through Day 28.
- Complete daily surveys to review objective data (sleep duration and sleep latency) from wearable device collection and answer questions about their prior night's sleep quality and level of alertness since waking.
- Administer nightly dose of study product 30-60 minutes prior to lying down in bed through Day 14.

No Product Use Period (Day 15 to Day 21):

- Complete Insomnia Severity Index and Generalized Anxiety Disorder-7 (Day 15 only).
- Continue nightly use of personal health tracking wearable device through Day 28.
- Complete daily surveys to review objective data (sleep duration and sleep latency) from wearable device collection and answer questions about their prior night's sleep quality and level of alertness since waking.

Product Use Period (Day 22 to Day 28):

- Complete Insomnia Severity Index and Generalized Anxiety Disorder-7 (Day 22 only).
- Continue nightly use of personal health tracking wearable device through Day 28.
- Complete daily surveys to review objective data (sleep duration and sleep latency) from wearable device collection and answer questions about their prior night's sleep quality and level of alertness since waking.

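### With a two-week look-back and weekly on/off periods, no ISI score isolates the no-product week, so the secondary ISI contrast with that week cannot be measured cleanly

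*Combined protocol and SAP*

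**What the plan says.** Section 1.0 lists as a secondary endpoint "Change in Insomnia Sleep Index (ISI) by 4.5 points from baseline and 1 week of no product use". Section 2.2 gives the instrument's look-back: "perception of both nocturnal and diurnal symptoms of insomnia during the past two weeks".

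Section 3.3 sets the product cycle: "2 weeks of product use (1 week on - 1 week off - 1 week on". Section 6.1 dates it: product on Days 8–14, none on Days 15–21, product again on Days 22–28. The same section and Table 4.1 place the ISI on Days 1, 8, 15, 22 and 29. Each ISI is listed at the start of a period. For example, the second product period opens with "Complete Insomnia Severity Index and Generalized Anxiety Disorder-7 (Day 22 only", although that score can only look back on earlier nights. The baseline week carries the instruction "Begin discontinuation of non-prescription products used for sleep".

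Section 9.1 claims at least 90% power for a 4.5-point ISI change with SD 5, without naming the contrast. Section 9.6 spells out a comparison only for the sleep quality VAS (baseline against end of study). It does not say how the ISI contrast is formed. Nothing in the plan shortens the ISI recall or deals with overlapping windows.

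**The concern.** A contrast between product and no product needs scores that differ in exposure. If the look-back is twice the length of a period, the ISI closing the no-product week also covers the product week before it, and the ISI closing the second product week also covers the no-product week. The two scores then share nights and may have the same exposure. A small or null ISI difference could be reported as absence of effect when it partly reflects the recall window, and readers could take section 9.1 as assurance that the contrast was well powered.

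**Working it through.** **1. The plan's own figures.** SD of a paired difference = SD × √(2(1 − r)). For the VAS (SD 2, r = 0.5) this is 2 × √1 = 2. A paired t-test for a difference of 1 at two-sided 0.05 and 90% power needs 44. Dividing by the Wilcoxon efficiency 3/π gives 46.1, so 47, as stated; power at 47 is 90.6%. For the ISI, a measured 4.5-point change with SD of difference 5 (SD 5 with r = 0.5) has power above 99.9% at 47. The section 9.1 statement therefore reproduces.

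**2. Exposure in each window.** Inputs: a 14-night look-back (section 2.2), and product nights 8–14 and 22–28 (section 6.1).

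| ISI | Nights covered | Product nights, earlier week | Product nights, latest week | Total of 14 |
|---|---|---|---|---|
| Day 1 | −13 to 0 | 0 | 0 | 0 |
| Day 8 | −6 to 7 | 0 | 0 | 0 |
| Day 15 | 1 to 14 | 0 | 7 | 7 |
| Day 22 | 8 to 21 | 7 | 0 | 7 |
| Day 29 | 15 to 28 | 0 | 7 | 7 |

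The Day 22 and Day 29 windows share nights 15–21. This step needs no assumption beyond the documents.

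**3. What the contrast shows.** Let w be the weight a respondent gives the latest week (not in the documents) and E the improvement from a week of product. Assume additivity, one w for everyone, and no trend or carryover. Expected improvement is wE on Day 15, (1 − w)E on Day 22 and wE on Day 29. So Day 29 minus Day 22 shows wE − (1 − w)E = (2w − 1)E. The Day 15/29 average minus Day 22 shows the same.

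Power below uses E = 4.5, n = 47, SD 5, r = 0.5 (stated for the VAS only) and a two-sided 0.05 Wilcoxon test by the efficiency method. SD of difference is 5.00 for one day and 5 × √(1.5 × 0.5) = 4.33 for the average, assuming equal correlations.

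| w | (2w − 1) × 4.5 | Power, Day 29 − Day 22 | Power, average − Day 22 |
|---|---|---|---|
| 0.5 | 0 | 5% | 5% |
| 0.6 | 0.90 | 22% | 28% |
| 0.7 | 1.80 | 65% | 78% |
| 0.75 | 2.25 | 84% | 93% |
| 0.9 | 3.60 | over 99% | over 99% |
| 1 | 4.50 | over 99.9% | over 99.9% |

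Below w = 0.5 the sign reverses: at w = 0.4 the contrast is −0.9.

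**4. Weight needed for 90% power.** The measured difference required is 2.47 points (one day) or 2.14 (average). Solving (2w − 1) × 4.5 for these, unrounded, gives w = 0.775 and 0.738. At r = 0, 0.3 and 0.7 the one-day thresholds are about 0.89, 0.83 and 0.71; for the average they are 0.84, 0.78 and 0.68.

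**5. Change from baseline.** The product component of Day 29 minus a pre-product ISI is wE. At w = 0.5 that is 2.25 points, with power 84% at r = 0.5 (55% to 97% for r from 0 to 0.7). Nights before Day 1, when the stopping of other sleep products begins, make up 14 of 14 in the Day 1 window, 7 of 14 in the Day 8 window and 0 of 14 in the Day 29 window.

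**The case against.** **Respondents probably favour recent nights.** This is plausible. Section 2.2 lists an item on "satisfaction with current sleep pattern", which reads as present state, so w = 0.5 on every item is an extreme. If w is near 0.75 or above, little power is lost, and 90% does not require respondents largely to ignore the earlier week: a 22% to 26% weight on it is compatible with 90% at r = 0.5. This limits the size of the problem, but the contrast is undistorted only at w = 1.

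**The size is not in the documents.** That is true. Neither w nor the ISI correlation is given, SD 5 may already be the SD of change, and section 9.6 does not define the ISI contrast. Day 29 minus Day 22 is one natural reading of section 1.0. The exposure counts do not depend on any of this.

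**A reader might infer that the contrast is always biased toward zero.** The documents do not support that. The sign reverses below w = 0.5, and a time trend or carryover would alter the result.

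**A reader might infer that change from baseline is also biased toward zero overall.** Only its product component is diluted. Without a concurrent control, and with participants selected for a high screening ISI, regression to the mean or general improvement could enlarge it. The stopping of other sleep products acts in an unknown direction.

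**The mixed models in section 9.6 handle correlated data.** They do, but modelling correlation does not separate weeks that a single score mixes. Explicit current-week and prior-week exposure terms could help, and none is specified.

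**It is one contrast of one secondary endpoint.** This stands and sets the priority.

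**Conclusion.** The mismatch is certain on the plan's own text: the Day 15, 22 and 29 ISIs each look back on 7 product and 7 non-product nights, and no ISI isolates the no-product week or a product week. The secondary contrast with that week should not be tested and interpreted as written.

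The size of the distortion is illustrative. It rests on an unknown w, an additive effect, no trend or carryover, and a correlation borrowed from the VAS. Under those assumptions the contrast is attenuated for w between 0.5 and 1, and at r = 0.5 one-day power reaches 90% only from about w = 0.78.

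Section 9.1 contains no arithmetic error. Its power figure holds for a measured 4.5-point change, but it does not in general describe a 4.5-point product effect against the no-product week. Nor is the wider on/off question lost: the daily sleep quality and alertness ratings and the wearable data are collected day by day and do not share the two-week look-back. The finding does not extend to the GAD-7, for which the documents give no recall period. It should be fixed, but it does not threaten the primary endpoint.

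**What to change.** Keep the two-week ISI and change wording in sections 1.0, 9.1 and 9.6, with IRB approval as section 12.1 requires:

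- Remove the no-product contrast from the ISI endpoint. Alternatively, keep it as descriptive only, stating the 7-of-14 overlap and that a null result is not evidence of no effect.
- Limit the ISI power statement to a measured change from baseline.
- Name in advance which pre-product ISI (Day 1 or Day 8) is compared with Day 29. Report the result as a change over a window half on product, with the number of baseline-window nights that precede Day 1.

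The cost is that one secondary contrast loses confirmatory status. Averaging Days 15 and 29 is not a substitute: it raises power when w exceeds 0.5 but leaves the expected contrast at (2w − 1)E.

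Two optional additions carry trade-offs the sponsor must weigh. A 7-day look-back on Days 8, 15, 22 and 29 would align windows with periods. It departs from the instrument as described, the documents do not support the 4.5-point and SD 5 assumptions for such a version, and its Day 8 window is the week in which other sleep products are being stopped. Current-week and prior-week exposure terms in the section 9.6 mixed model could serve as a sensitivity analysis. They assume no trend and cannot separate carryover from recall.

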3.0 SAMPLE SIZE, COHORT CHARACTERISTICS, ELIGIBILITY AND INVOLVEMENT

3.1 Sample Size and Cohort Characteristics

The sample size for this study will be 47 volunteers who meet the participant eligibility.

